6.2 IMPORTANT PROTOCOL DEVIATIONS

Handling of iPDS in analysis is included in the DV domain specifications and stored within the TMF in EDMS.

6.3 SUBJECT SETS ANALYSED

- Screened Set:

This subject set includes all patients who have signed the informed consent. The screened set is used for patient disposition tables.

- Treated Set (TS):

This subject set includes all patients who were dispensed study medication and were documented to have taken at least one dose of investigational treatment. The treated set is used for both efficacy analyses and safety analyses.

- MTD Set:

This subject set includes all patients evaluable for MTD in the dose escalation part of the trial, who were not replaced within the MTD evaluation period. Replaced patients will also be included (refer to CTP Section 3.3.4.1.2 for criteria for being evaluable for MTD). The MTD set will be used for Bayesian Logistic Regression Models (BLRMs).

- PK Analysis Set (PKS):

This subject set includes all patients in the treated set who provided at least one evaluable observation for at least one PK endpoint and were not excluded due to a protocol deviation relevant to the evaluation of PK or due to PK non-evaluability. Analyses of PK parameters will be based on the PKS. The PKS will be used for statistical pharmacokinetic analyses.

Plasma concentrations and/or parameters of a patient will be considered as nonevaluable, if for example

- 1) The patient experienced emesis that occurred at or before two times median t_{max} of the respective treatment (Median t_{max} is to be determined excluding the patients experiencing emesis),
- 2) A predose concentration is $>5\%$ C_{max} value of that patient in the respective treatment period
- 3) Missing samples/concentration data at important phases of PK disposition curve

■ [REDACTED]

[REDACTED]

[REDACTED]

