## FLOW CHART

Trial period	SCR	BI 3011441 monotherapy treatment period									EO T q	EOR r	Extended FU for progressive disease s
Cycle a		C1 t							C 2	C3+			Every 8 weeks
Visit number	SCR	1	2	3	4	5	6	7	1	1	EO T	EOR	
Treatment day	Up to 28 days b	1	2	3	8	15 ±1	16	22 ±3	1 ±2	1 ±2		30 d after treat. disc. (+1 wk)	±4 days
Informed consent	x												
Inclusion / exclusion criteria	x	x											
Medical history and demographics	x												
Report planned hospitalisations	x												
Physical examination, height (screening only), and weight c	x	x							x	x	x	x	x
ECOG Performance score c	x	x				x			x	x	x	x	x
Issue patient diary d		Continuous											
12-Lead Electrocardiograms (triplicate) e	x	x				x	x		x	x	x		
LVEF f	x					x			x	x	x		
Vital signs	x	x	x	x	x	x	x	x	x	x	x	x	
Pregnancy test g	x	x							x	x	x		
Safety laboratory (haematology, biochemistry, urine, virology) g	x	x			x	x	x	x	x	x	x		
Safety laboratory (coagulation) g	x	x							x	x	x		
Ophthalmological assessment h	x								x	x	x		
Tumour assessment i	x								x	x			x
Blood sampling for pharmacokinetics j		x	x		x	x	x	x	x	x			
													
													
Archival tumour tissue l	x												
BI 3011441 intake m		Continuous daily treatment until progression											
Concomitant therapy	x	x	x	x	x	x	x	x	x	x	x	x	x
All AEs/SAEs/AESIs n	x	x	x	x	x	x	x	x	x u	x	x	x	x
Vital status o											x	x	
Eligibility for next treatment cycle p									x	x			

Proprietary confidential information © 2020 Boehringer Ingelheim International GmbH or one or more of its affiliated companies

- a) Treatment cycles (C) are 28 days (4 weeks). Patients will continue treatment with BI 3011441 as long as they are deriving clinical benefit or until undue drug toxicity or withdrawal of consent, whichever occurs first.
- b) Screening should take place within 28 days of start of trial treatment.

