- i) Tumour assessments should be done according to RECIST v1.1 and should include computed tomography (CT) scans of the chest and abdomen and, if clinically indicated, imaging of any other known or suspected sites of disease (e.g., pelvis, brain) using an appropriate method (CT scan or magnetic resonance imaging [MRI]). See [Section 5.1](#) for detail.
- j) PK sample (plasma [REDACTED]) will be collected at timepoint indicated in [Table 10.1: 1](#).  
k) [REDACTED]
- l) Archival formalin-fixed paraffin-embedded (FFPE) tumour tissue from most recent timepoint (preferred less than 6 month old) should be collected. See Section 5.4 and [Table 5.4.1: 1](#) for further details.
- m) BI 3011441 intake is daily. Dosing of BI 3011441 will be determined by the SMC and communicated separately as each new cohort opens for recruitment.
- n) DLTs will be collected throughout the trial and will be assessed for dose-escalation decisions following the first cycle. All serious adverse events (SAEs) and adverse events of special interest (AESIs) considered trial treatment related, cancers of new histology and exacerbations of existing cancer (see [section 5.2.6.2.1](#)) must be collected in the extended follow-up period.
- o) Patients who discontinue trial treatment prematurely and have agreed to be contacted, should be called at least at the end of their scheduled trial participation to obtain their vital status information, please see [Section 5.2.6.2.1](#)
- p) Before initiating a new treatment cycle, criteria should be checked, please see [Section 4.1.4.1](#)
- q) An EOT visit should be performed for all patients who permanently discontinued trial medication. If the decision to permanently discontinue treatment is taken at a scheduled visit, the EOT visit should be performed instead of the scheduled visit (preferably within 7 days after the last treatment).
- r) Residual effect period (REP) starts after last dose of trial medication and ends 30 days later. Whenever possible, a 30-day safety FU visit should take place before any other anti-cancer treatment starts.

Proprietary confidential information © 2020 Boehringer Ingelheim International GmbH or one or more of its affiliated companies

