## 10. APPENDICES

### 10.1 TIME SCHEDULE FOR PHARMACOKINETIC (PK) SAMPLING

Table 10.1: 1 Time schedule for PK blood [REDACTED] sampling and ECG

Cycle	Visit	Day	Time Point [hh:min]	CRF Time /PTM	Event		
					Drug administr.	PK Blood and ECG	[REDACTED]
1	1	1	Just before drug administration	-0:05		X	[REDACTED]
			0:00	0:00	X		[REDACTED]
			0:30	0:30		X	[REDACTED]
			0:45	0:45		X	[REDACTED]
			1:00	1:00		X	[REDACTED]
			1:30	1:30		X	[REDACTED]
			2:00	2:00		X	[REDACTED]
			2:30	2:30		X	[REDACTED]
			3:00	3:00		X	[REDACTED]
			4:00	4:00		X	[REDACTED]
			6:00	6:00		X	[REDACTED]
			8:00	8:00		X	[REDACTED]
			10:00	10:00		X	[REDACTED]
			12:00	12:00		X a	[REDACTED]
2	2		Just before drug administration	23:55		X	[REDACTED]
4	8		Just before drug administration	167:55		X	[REDACTED]
5	15	15	Just before drug administration	335:55		X	[REDACTED]
			0:00	336:00	X		[REDACTED]
			0:30	336:30		X	[REDACTED]
			0:45	336:45		X	[REDACTED]
			1:00	337:00		X	[REDACTED]
			1:30	337:30		X	[REDACTED]
			2:00	338:00		X	[REDACTED]
			2:30	338:30		X	[REDACTED]
			3:00	339:00		X	[REDACTED]
			4:00	340:00		X	[REDACTED]
							[REDACTED]
			6:00	342:00		X	[REDACTED]
			8:00	344:00		X	[REDACTED]
			10:00	346:00		X	[REDACTED]
			12:00	348:00		X a	[REDACTED]

Table 10.1: 1 Time schedule for PK blood [REDACTED] sampling and ECG (cont.)

Cycle	Visit	Day	Time Point [hh:min]	CRF Time /PTM	Event		
					Drug administr.	PK Blood and ECG	[REDACTED]
	6	16	Just before drug administration	359:55		X	[REDACTED]
	7	22	Just before drug administration	503:55		X	
2	1	1	Just before drug administration	-0:05		X	
3	1	1	Just before drug administration	-0:05		X	
4	1	1	Just before drug administration	-0:05		X	

a) An optional 12-hour postdose PK blood sample should be collected if the patient is willing.

b) [REDACTED]

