5.2.2 Secondary endpoints

The secondary endpoints are, as specified in CTP Section 2.1.3:

- Number of patients with DLTs during the entire on-treatment period
- Number of patients with Grade ≥ 3 treatment-related adverse events
- Number of patients with treatment related adverse events at each dose level
- Pharmacokinetic parameters of BI 3011441: $C_{max,ss}$, and $AUC_{0-tz,ss}$

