6.6 HANDLING OF MISSING DATA AND OUTLIERS

Every effort should be made to collect complete data at each visit for each patient. If not specified otherwise, missing data will not be imputed and remain missing. Potential outliers will be reported and analysed as observed.

Missing or incomplete AE dates are imputed according to BI standard (see “Handling of missing and incomplete AE dates”) (2)

Missing data and outliers of PK data are handled according to the relevant BI standard (see BI-KMED-TMCP-MAN-0012: “Standards and processes for analyses performed within Clinical Pharmacokinetics/Pharmacodynamics” (5) and BI-KMED-TMCP-MAN-0014

“Noncompartmental Pharmacokinetic / Pharmacodynamic Analyses of Clinical Studies” (6)). PK parameters that cannot be reasonably calculated based on the available drug concentration-time data will not be imputed.

In general, missing data not discussed in (2) and (6) will not be imputed unless required for the following analyses and definitions. Then the rules as described below apply.

Change of laboratory values from baseline

Laboratory values at baseline: For missing laboratory data at cycle 1 day 1 (before the first administration of any study medication) the data of preceding visits will be used if available.

Definition of on-treatment period and actual treatment

Date of permanent discontinuation of study medication: All reasonable efforts should be undertaken during the study to obtain the dates of permanent discontinuation of study medication. However, if the date of the very last administration is missing this will be imputed with:

- If only month and year are given, the last day of the month will be used for imputation
- If only the year is given, the 31st of December of this year will be used for imputation

If the imputed date leads to a date that is later than the date of the EOT visit, then the imputed date is the date of the EOT visit. If the imputed date leads to a date that is later than the death date, then the imputed date is the date of death.

Partial death dates

If a partial (year and month) death date is reported, the date will be imputed with the end of the month for the analysis of PFS. This is in line with the imputation of partial dates for the analysis of AEs.

Partial or missing start date of subsequent anti-cancer therapy/subsequent radiotherapy

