The ADS “ADPP” (PK parameters) contains column variables APEX and APEXCO indicating inclusion/exclusion (APEX) of a PK parameter and an analysis flag comment (APEXCO). All analyses based on the PKS will include parameters if they are not flagged for exclusion, that is APEX is equal to “Included”.

Exclusion of PK concentrations

The ADS “ADPC” (PK concentrations per time-point or per time-interval) contains column variables ACEX and ACEXCO indicating inclusion/exclusion (ACEX) of a concentration and an analysis flag comment (ACEXCO). Exclusion of a concentration depends on the analysis flag comment ACEXCO. For example, if ACEXCO is set to ‘ALL CALC’, the value will be excluded for all types of analyses based on concentrations. If ACEXCO is set to ‘DESC STATS’ the value will be excluded from descriptive evaluations per planned time point/time interval. If ACEXCO contains the addition ‘TIME VIOLATION’ or ‘TIME DEVIATION’ the value can be used for further analyses based on actual times. If ACEXCO is set to ‘HALF LIFE’, the value will be excluded from half-life calculation (and, as a consequence, any calculation that relies on λz) only; the value is included for all other analyses. Further details are given in BI-KMED-TMCP-MAN-0014 “Noncompartmental Pharmacokinetic / Pharmacodynamic Analyses of Clinical Studies” (6) and BI-KMEDTMCP-MAN-0010: “Description of Analytical Transfer Files and PK/PD Data Files” (7).

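### SAP 6.3 does not limit the PK predose criterion (above 5% of Cmax) to the sample before the first dose; applied as worded to the Day 15 trough, it could exclude valid steady-state values

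*SAP*

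**What the plan says.** SAP 6.3 defines the PK Analysis Set and then lists grounds for setting data aside: "Plasma concentrations and/or parameters of a patient will be considered as nonevaluable, if for example". Criterion 2 is a predose concentration above 5% of the Cmax "value of that patient in the respective treatment period". It names no day, cycle or first dose, and makes no exception for steady state.

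The surrounding design is as follows.

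- **Endpoints.** SAP 5.2.2 lists "Pharmacokinetic parameters of BI 3011441", and the two parameters shown are both steady-state values: Cmax,ss and AUC0-tz,ss.
- **Dosing.** Footnote m of the Protocol Flow Chart states "BI 3011441 intake is daily".
- **Sampling.** Protocol Table 10.1: 1 schedules samples marked "Just before drug administration" on Days 1, 2, 8, 15, 16 and 22 of Cycle 1 and on Day 1 of Cycles 2, 3 and 4. The only full profile after repeated dosing is on Day 15, and it opens with the predose sample at 335:55.
- **Treatment period.** The Flow Chart has a single heading, "BI 3011441 monotherapy treatment period". SAP Table 6.1: 1 defines periods for safety analysis only.
- **Delegation.** For the exclusion flags, SAP 7 adds "Further details are given in BI-KMED-TMCP-MAN-0014". SAP 6.6 says "Missing data and outliers of PK data are handled according to the relevant BI standard". SAP 6.3 cites no manual for criterion 2.

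**The concern.** A limit of 5% of Cmax on a predose sample works as a carry-over check. It is informative where no drug should be present, which in this trial is only before the first administration. At every later predose time the patient should already have drug in plasma, and a value above 5% of Cmax may be ordinary accumulation.

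The wording allows three readings:

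- **(a)** Only the sample before the first dose of the single treatment period is tested. This is harmless.
- **(b)** Each profile is tested against its own predose sample. The Day 15 trough then decides whether that patient's Cmax,ss and AUC0-tz,ss count.
- **(c)** Any predose sample during treatment is tested. Other values of the same patient, including Day 1, could then be affected as well.

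Under (b) or (c), valid steady-state values could be lost in a trial of about 12 patients that has characterising PK in Japanese patients as a secondary objective. Whether a patient is kept would depend on that patient's half-life, so the loss would not be random.

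**Working it through.** The plan gives no figure of its own to reproduce here. The check is a count of samples, followed by a model of when a trough passes 5%.

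**Step 1: count.** Table 10.1: 1 has 6 predose samples in Cycle 1 and 3 in Cycles 2 to 4, so 9 in all. One precedes all dosing; the other 9 − 1 = 8 follow earlier doses.

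**Step 2: inputs for the model.** From the documents: dosing interval τ = 24 h, sampling times 0 to 12 h after the dose, and predose samples 5 minutes before the next dose (23.92 h). Assumed, because the clinical PK part of Protocol 1.2 is not readable: half-life, one-compartment kinetics, and tmax of 1 to 3 h.

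**Step 3: simplest threshold.** With mono-exponential decline over time t from the peak to the next predose sample, trough/Cmax = 2^(−t/half-life). This exceeds 1/20 when half-life > t / log2(20), where log2(20) = 4.32.

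- t = 24 h: 24 / 4.32 = 5.55 h.
- t = 22 h (peak 2 h after the dose): 22 / 4.32 = 5.09 h.

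**Step 4: threshold with oral absorption.** At steady state, C(t) is proportional to ka/(ka − k) × [e^(−kt)/(1 − e^(−kτ)) − e^(−ka·t)/(1 − e^(−ka·τ))], with k = ln 2 / half-life and ka set to give the assumed single-dose tmax, ln(ka/k)/(ka − k). Cmax is the largest value at the scheduled times. I solved for trough/Cmax = 5%:

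| Assumed tmax | Half-life threshold, Day 15 | Half-life threshold, Day 2 trough over Day 1 Cmax |
|---|---|---|
| 1 h | 5.24 h | 5.23 h |
| 2 h | 4.88 h | 4.87 h |
| 3 h | 4.41 h | 4.40 h |

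Steps 3 and 4 together give a Day 15 threshold of about 4.4 to 5.6 h. The last column shows that reading (c) would begin to bite at almost the same half-life.

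**Step 5: how many of 12 would keep steady-state values under reading (b).** Half-life and ka are taken as lognormal, each with CV 30% or 50%; median tmax is 1, 2 or 3 h; there are 200,000 simulated patients per setting; a patient is kept if trough/Cmax is at most 5%.

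| Median half-life | Expected number kept of 12 |
|---|---|
| 4 h | 6.5 to 9.8 |
| 6 h | 2.1 to 4.6 |
| 8 h | 0.4 to 2.2 |

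At 12 h at most 0.5 would be kept. At 3 h it would be 8.4 to 11.6. The result therefore runs from little loss to nearly total loss, depending on a half-life that the public text does not give.

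**The case against.** The best defence is that reading (a) is the natural one. The criterion speaks of a treatment period, the Flow Chart shows only one, and a plan should be read so that its parts fit: the SAP would hardly specify steady-state endpoints and then discard them for having troughs. The list is also introduced as examples, and exclusion works through flags with comments on individual values. Internal PK manuals govern much of the PK handling, and redacted text directly follows the criteria. Either may already limit the rule.

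Most of this stands. It means that readings (b) and (c) are possible but not shown to be intended. It does not remove the point. The sentence says that such data will be considered nonevaluable, and calling the list illustrative makes it longer, not narrower. Elsewhere the SAP does state a first-dose limit when it means one, as in the rule for baseline laboratory values in SAP 6.6. No visible passage does so for criterion 2.

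A reader might go further and infer that the trial will lose its steady-state results. The documents do not support that: neither the half-life nor the manuals can be seen. Nor do they support a claim that whole patients would leave the PK set, because exclusion can operate on single concentrations or parameters.

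**Conclusion.** The wording of criterion 2 is ambiguous in a way that could matter, and it should be tightened. Under the harmless reading nothing is lost. Applied as worded to the Day 15 profile, it would exclude valid Cmax,ss and AUC0-tz,ss values once the half-life exceeds about 4.4 to 5.6 h. That figure rests on one-compartment kinetics with an assumed tmax of 1 to 3 h, or on mono-exponential decline; the numbers kept also rest on 12 patients and a CV of 30 to 50%.

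It is tempting to say that the exposure summaries would be biased low because patients with long half-lives drop out. That does not follow. Half-life may differ between patients through clearance or through volume of distribution, and these need not move Cmax,ss and AUC0-tz,ss in the same direction, so no direction of bias can be stated.

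Severity is minor. The PK endpoints are summarised descriptively, individual PK values are also reported in the trial report, and the MTD analysis does not use them.

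**What to change.** In SAP 6.3, limit criterion 2 to the predose sample before the first administration (Cycle 1 Day 1). Add that a trough above 5% of Cmax on a later day is not by itself a reason to exclude steady-state concentrations or parameters. If an internal PK manual already contains this rule, cite it in SAP 6.3 instead. The other criteria can stay as they are.

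The cost is one or two sentences, with no new data and no design change. It is best done before the PK exclusion flags are set.

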6.5 POOLING OF CENTRES

This section is not applicable because centre/country is not included in the statistical model.

6.6 HANDLING OF MISSING DATA AND OUTLIERS

Every effort should be made to collect complete data at each visit for each patient. If not specified otherwise, missing data will not be imputed and remain missing. Potential outliers will be reported and analysed as observed.

Missing or incomplete AE dates are imputed according to BI standard (see “Handling of missing and incomplete AE dates”) (2)

Missing data and outliers of PK data are handled according to the relevant BI standard (see BI-KMED-TMCP-MAN-0012: “Standards and processes for analyses performed within Clinical Pharmacokinetics/Pharmacodynamics” (5) and BI-KMED-TMCP-MAN-0014

“Noncompartmental Pharmacokinetic / Pharmacodynamic Analyses of Clinical Studies” (6)). PK parameters that cannot be reasonably calculated based on the available drug concentration-time data will not be imputed.

In general, missing data not discussed in (2) and (6) will not be imputed unless required for the following analyses and definitions. Then the rules as described below apply.

Change of laboratory values from baseline

Laboratory values at baseline: For missing laboratory data at cycle 1 day 1 (before the first administration of any study medication) the data of preceding visits will be used if available.

Definition of on-treatment period and actual treatment

Date of permanent discontinuation of study medication: All reasonable efforts should be undertaken during the study to obtain the dates of permanent discontinuation of study medication. However, if the date of the very last administration is missing this will be imputed with:

- If only month and year are given, the last day of the month will be used for imputation
- If only the year is given, the 31st of December of this year will be used for imputation

If the imputed date leads to a date that is later than the date of the EOT visit, then the imputed date is the date of the EOT visit. If the imputed date leads to a date that is later than the death date, then the imputed date is the date of death.

Partial death dates

If a partial (year and month) death date is reported, the date will be imputed with the end of the month for the analysis of PFS. This is in line with the imputation of partial dates for the analysis of AEs.

Partial or missing start date of subsequent anti-cancer therapy/subsequent radiotherapy

If the day of the start date of subsequent systemic therapy/subsequent radiotherapy is missing, then the 1st of the month will be imputed unless this leads to a date before the stop date of study medication. In this case the stop date of study medication +1 day will be imputed.

If day and month, or day and month and year are missing, it will be distinguished whether the start date of subsequent systemic therapy/subsequent radiotherapy is required for censoring of PFS or for other descriptive statistics:

- **For censoring of PFS:** If only the year is reported, the 1st of January of this year will be imputed unless this leads to a date before the stop date of study medication. In this case the stop date of study medication +1 day will be imputed. In case of a completely missing start date of subsequent anti-cancer therapy/subsequent radiotherapy and the patient did not have any post-baseline tumour assessment or did not progress or die, the PFS of this patient will be censored at the day of first administration of study drug. Additionally, all imputed start dates of subsequent anti-cancer therapy/subsequent radiotherapy should be before death date, if available.
- **For descriptive statistics:** Dates will not be imputed if more than only the day of the date is missing.

6.7 BASELINE, TIME WINDOWS AND CALCULATED VISITS

Unless otherwise specified baseline is defined as the time point closest to but prior to the first administration of any study medication. If no time is specified and the date is the same as the first administration date, then it will still be considered baseline if not specified otherwise. If there is no measurement earlier than the first administration of study medication, then no baseline will be derived.

For laboratory parameters for which not only the examination date but also the sampling time was recorded, examination time should be taken into consideration when defining baseline. That is a laboratory measurement on the same date as the first administration of study treatment is considered as baseline if and only if the examination time of this laboratory measurement is before the first administration of study treatment. If any of these times is missing and the date of laboratory assessment is the same as the date of first administration of study medication, then the laboratory assessment will be considered as according to protocol, i.e., as prior to first study medication.

Study days and visits will be labelled according to the flow charts in the CTP. Study day will be calculated relative to the date of the first administration of study drug. The day prior to first

administration of study drug will be 'Day -1' and the day of first administration of study drug will be 'Day 1'; therefore 'Day 0' will not exist.

Imaging time windows:

Time windows and visits will be calculated to determine the planned day of tumour measurement and response status, based on the protocol-specified tumour imaging schedule.

For the presentation of tumour response data which will follow a calculated visit approach based on the protocol specified tumour imaging schedule: Imaging will be performed at screening and every 8 weeks after the first administration of study treatment (i.e. Week 8, 16, 24 etc.). Image data will be slotted to Week 8, 16, 24 etc. based on their relative study day (from start of treatment) and using a ± 4 week window (e.g., images taken in the first 6 weeks from start of treatment will be assigned to Week 8). If two or more images for a patient are assigned to one interval then the last assessment will be used to ensure PD is not missed.

In order to identify whether consecutive imaging time points are missing for a given patient, a nominal time point (i.e. Week 8, 16, 24 etc.) will be assigned to each and every image. This is achieved by creating windows for every radiological response assessment. These windows are defined in [Table 6.7: 1](#). If a patient does not have an image in one of the windows described above, the patient will be considered to have missed an assessment for that time point.

Table 6.7: 1 Nominal time points and windows for imaging

Nominal time point (weeks from start of study medication)	Target day of the scan (study day)	Window (study day)
8	57	1 to ≤ 85
16	113	86 to ≤ 141
24	169	142 to ≤ 197
32	225	198 to ≤ 253
40	281	254 to ≤ 309
48	337	310 to ≤ 365
56	393	366 to ≤ 421
Etc., 8 week interval	Etc.	Etc.

NOTE: The date of the first dose of study medication is Day 1

